## **4.3 Interim analyses and data monitoring**

No formal interim analysis is planned for PD0049. Also, no specific data monitoring, steering, or evaluation committee is planned for this study.

## **4.4 Multicenter studies**

No multicenter analyses are planned. Therefore, this section is not applicable for this study.

## **4.5 Multiple comparisons/multiplicity**

All statistical tests are considered exploratory, and calculated p-values  $<0.05$  do not indicate statistical significance, since no alpha adjustment will be performed.

## **4.6 Use of an efficacy subset of subjects**

The FAS will be used as primary analysis set for efficacy analyses. The primary efficacy analyses will be repeated for the PPS. The PPS will be used to evaluate subjects who have efficacy data and are reasonably compliant with the conditions of the study. This analysis set will

---

provide additional information on the efficacy analysis and will describe findings in a subset of subjects who more closely followed the intentions of the study protocol.

#### **4.7 Active-control studies intended to show equivalence**

This section is not applicable for this study.

#### **4.8 Examination of subgroups**

No subgroups are defined for this study.

### **5 STUDY POPULATION CHARACTERISTICS**

#### **5.1 Subject disposition**

Subject disposition will be summarized on all subjects screened. The number of subjects screened, in addition to the number and percentage of those subjects who were screen failures, broken down by primary reason for screen failure, will be presented.

A summary of disposition of subjects will be provided for all screened subjects. The date of first subject in, date of last subject out, number of subjects screened, and the number of subjects in each analysis set by group and for all subjects will be summarized overall and by investigator site. Subjects who transferred sites will be summarized according to their original site.

A summary of disposition of analysis sets will be provided for the SS. Additionally, a summary of disposition and discontinuation reasons will present the number and percentage of subjects starting the study, completing the study, and discontinuing the study with primary reason for discontinuation.

A summary of discontinuations due to AEs for the SS will present the number and percentage of subjects who discontinued this study due to AEs broken down by type of AE.

The following listings will be provided: study eligibility criteria text, subjects who did not meet study eligibility criteria, subject disposition, subject analysis sets, Neupro discontinuation and visit dates.

#### **5.2 Protocol deviations**

Important protocol deviations defined in the protocol-specific document, and additionally identified at the data evaluation meetings, will be listed. In addition, the number and percentage of subjects with at least 1 important protocol deviation will be summarized overall and by category of important protocol deviation for the SS. The number and percentage of subjects with no important protocol deviations will also be summarized for the SS. These will be summarized by group and for all subjects overall. A listing of important protocol deviations will be provided.

## 6 DEMOGRAPHICS AND OTHER BASELINE CHARACTERISTICS

### 6.1 Demographics

Tables with descriptive statistics and listings will be given for the demographic variables age, gender, weight and height at Baseline, race, ethnicity, and body mass index (BMI). Demographic characteristics will be summarized for all study defined analysis sets, and presented in a listing.

The calculation of age is based on the date of informed consent and the date of birth. If the date of birth is incomplete, it will be completed with January as imputed month if month is missing and it will be completed with 1 as imputed day of birth if day is missing. Age is calculated as follows: Age (years) = ([Date of Informed Consent] – [Imputed Date of Birth]) / 365.25. It will be summarized as a continuous variable and as a categorical variable based on the categories: <65 years, 65-<85 years, ≥85 years, also based on the categories: <65 years, ≥65 years, and also based on the categories: <75 years, ≥75 years.

Weight recorded in pounds (lb) will be converted to kilograms (kg) as weight(lb)\*0.4536kg/lb.

Height recorded in inches (in) will be converted to height in centimeters (cm) as height(in)\*2.54cm/in.

The BMI will be calculated using the following formula (Keys et al, 1972):

$$\text{BMI (kg/m}^2\text{)} = 10000 * \frac{\text{weight (kg)}}{[\text{height (cm)}]^2}$$

### 6.2 Other Baseline characteristics

The disease stage of Parkinson's Disease at Baseline can be assessed by the given start dose of Neupro at either 2mg/24h or 4mg/24h. The start dose of Neupro is tabulated within the study medication summary.

### 6.3 Medical history and concomitant diseases

Medical history data and concomitant diseases data are not collected. Therefore this section is not applicable.

### 6.4 Prior and concomitant medications

Medications will be considered as prior if the start date of the medication is before the date of first patch administration. Medications will be considered as concomitant if they are taken at least once in the treatment period starting with the first patch administration and ending after the last patch administration during the study. Medications starting prior to first patch administration and continuing into the treatment period will be considered both prior and concomitant medication.

In case of partial or missing dates the rules described in [Section 4.2](#) will be applied.

Prior and concomitant medications will be summarized separately for the SS. The number and percentage of subjects who used prior and concomitant medications, respectively, will be presented according to the anatomical main group (level 1), the pharmacological subgroup (level 3), and the preferred term.

## 7 MEASUREMENTS OF TREATMENT COMPLIANCE

A calculation of treatment compliance will not be performed. This is due to the nature of this pilot study. Subjects in both treatment arms are treated using standard clinical practice only, there is no fixed mandatory dosing scheme to be followed. Also, no diary data or drug accountability data is collected. Data on Neupro dosing is recorded on the concomitant medication pages of the CRF only. Given this, an appropriate measure for treatment compliance could not be identified.

## 8 EFFICACY ANALYSES

The efficacy analysis will be performed on the FAS and observed cases will be utilized. The PPS will be used for sensitivity analysis on selected efficacy variables.

### 8.1 Statistical analysis of the primary efficacy variables

The change from Baseline to Visit 2 in the primary efficacy variables will be analyzed for differences among the treatment groups using analysis of covariance (ANCOVA) with treatment group and center as factors and the corresponding baseline variable as a covariate. The 95% confidence interval (CI) on the calculated least square mean difference between experimental group and control group in change from baseline in the primary efficacy variables will also be reported.

#### 8.1.1 Derivations of primary efficacy variables

##### 8.1.1.1 Unified Parkinson's Disease Rating Scale Part III

The Unified Parkinson's Disease Rating Scale (UPDRS; Movement Disorder Society Task Force on Rating Scales for Parkinson's disease, 2003) consists of 4 parts: Part I of UPDRS assesses mentation, behavior, and mood. Part II of the UPDRS assesses the subject's activity of daily living. Part III assesses motor function. Part IV assesses complications of therapy.

The UPDRS Part III (motor subscale) will be measured in the "on" state and consists of 27 items and sub-items scored between 0 and 4. It includes speech, facial expression, tremor at rest (face, right hand, left hand, right foot, left foot), action or postural tremor of hands (right and left), rigidity (neck, extremities), finger taps (right and left), hand movements (right and left), rapid alternating movements of hands (right and left), leg agility (right and left), arising from chair, posture, gait, postural stability, body bradykinesia, and hypokinesia (14 items, 27 questions = 108 points maximum). The sum score will be calculated as sum of the 27 individual scores. If one or more items are missing, the sum score will also be missing.

##### 8.1.1.2 Kinesia-ONE variables

The Kinesia-ONE data includes the following variables collected at Baseline and at Visit 2:

- finger tapping speed score
- rest tremor score
- averaged finger tapping speed and resting tremor scores
- postural tremor score
- finger tapping amplitude score

- hand grasp speed score
- hand grasp amplitude score
- rapid alternating movement speed score
- rapid alternating amplitude score
- dyskinesia score
- kinetic tremor score
- rapid alternating movement rhythm score
- hand movements rhythm score
- finger tapping rhythm score

These scores are all calculated as an average from triplicate repeated assessments at a measurement point.

In addition, a composite Kinesia-ONE score will be calculated as the average of following scores:

- finger tapping speed score
- rest tremor score
- postural tremor score
- kinetic tremor score
- finger tapping amplitude score
- finger tapping rhythm score
- hand grasp speed score
- hand grasp amplitude score
- hand grasp rhythm score
- rapid alternating movement speed score
- rapid alternating amplitude score
- rapid alternating rhythm score

The composite score will only be calculated if at least 50% of the scores are available.

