12.6 Handling of dropouts or missing data

In general, there will be no imputation of missing data.

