## **2.2 Study variables**

### **2.2.1 Efficacy variables**

#### **2.2.1.1 Primary efficacy variables**

The primary efficacy variables of this study are:

- Change from Baseline (Visit 1/Week 1) to Visit 2 (Week 12/3 months after start of treatment with Neupro) in Unified Parkinson's Disease Rating Scale (UPDRS) Part III Motor Score
- Change from Baseline (Visit 1/Week 1) to Visit 2 (Week 12) in Kinesia-ONE variables:
  - finger tapping speed score
  - rest tremor score
  - averaged finger tapping speed and resting tremor scores
  - postural tremor score
  - finger tapping amplitude score
  - hand grasp speed score

- hand grasp amplitude score
- rapid alternating movement speed score
- rapid alternating amplitude score
- dyskinesia score
- kinetic tremor score
- rapid alternating movement rhythm score
- hand movements rhythm score
- finger tapping rhythm score
- average Kinesia-ONE score
- Neupro dose per 24h at Visit 2 (Week 12)
- Number of Neupro dose changes during the study (between Visit 1 and Visit 2)
- Discontinuation of treatment with Neupro during the course of the study

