## 3 DATA ANALYSIS CONSIDERATIONS

### 3.1 General presentation of summaries and analyses

The statistical analyses will be performed by Chiltern. Computations and generation of outputs will be performed using SAS® (Statistical Analysis System, SAS-Institute, Cary, NC, USA) Version 9.3 or above. All tables and listings will use Courier New font size 9.

For continuous data in general, summary statistics (n [number of available measurements], arithmetic mean, standard deviation (SD), median, minimum, and maximum) will be presented by group. For selected variables, the first (25th percent) quartile (Q1) and the third (75th percent) quartile (Q3) may also be presented (for patient reported outcomes).

Mean, SD, median and quartiles will be displayed to 1 more decimal place than collected in the source data. Derived variables in general will display the mean, SD and median to 1 more decimal place than the variables used in the derivation (i.e. a change from Baseline will be reported to the same precision as the Baseline data). However, a special rule can be defined as needed for appropriate reporting.

For descriptive statistics of continuous variables by visit, the change from Baseline and actual value at the given time point will be displayed. The change from Baseline is the post-Baseline value minus the Baseline value. If the Baseline or post-Baseline value is missing, then the change from Baseline is set to missing. Percent change from Baseline is the change from Baseline divided by Baseline and multiplied by 100. If the Baseline value is 0 and the post-Baseline value is also 0, then the percent change from Baseline is set to 0. If the Baseline value is 0 and the post-Baseline value is non-zero, then the percent change from Baseline is set to missing. If the Baseline value is missing, the percent change from Baseline is set to missing.

Frequency tables (frequency counts and percentages) will be presented for categorical data. If there are no missing values then the missing row can be removed. If there are missing values (including missing a single assessment or entire visit), then include the missing row with the frequency count and percentage. If there are no subjects in a specific CRF category, then that row will be retained and 0 presented in the table. In general, percentages will be calculated based on the utilized analysis set. However, in the case of subgroup analyses, the N of the subgroup will be used as denominator.

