### **8.1.2 Primary analysis of the primary efficacy variables**

The efficacy variables, change from Baseline to Visit 2 (for all continuous efficacy variables not based on Kinesia-360, i.e. UPDRS Part III and Kinesia-ONE scores) will be analyzed utilizing an analysis of covariance (ANCOVA) with Baseline as a covariate, “center” as factor, and “group” as main factor. The 2 groups are the Experimental Group (EG) and the Control Group (CG).

The 2-sided null and alternative hypotheses are:

- Null hypothesis ( $H_0$ ): EG=CG
- Alternative hypothesis ( $H_a$ ): EG $\neq$ CG

EG: Represents the change from Baseline to Visit 2 for subjects in the Experimental Group.

CG: Represents the change from Baseline to Visit 2 for subjects in the Control Group.

The efficacy analysis will be performed on the FAS and observed cases will be utilized. The group effect will be estimated and presented with 95% 2-sided CIs and p-values.

The single items of UPDRS Part III and the sum score will be presented in listings, the sum score will be summarized by group, and the change from Baseline to Visit 2 in UPDRS Part III score will be analyzed using ANCOVA.

The change from Baseline to Visit 2 in each of the Kinesia-ONE scores will be analyzed using ANCOVA.

The Neupro dose per 24h at Visit 2 will be summarized by group, as well as the Neupro starting dose per 24h. Both assessments of Neupro dose will be related in a shift table by group. In addition, Neupro dose and Neupro dose change will be tabulated as continuous variable.

The number of Neupro dose changes after first administration until Visit 2 will be summarized by group.

The comparison of the rate of discontinuation of treatment with Neupro during the course of the study for the control group and the experimental group will be performed using logistic regression with factors for treatment and center.

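### The Kinesia-ONE composite may average different components at Baseline and Visit 2, so its change score can differ from zero when no component has changed

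*SAP*

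**What the plan says.** SAP 2.2.1.1 lists the "average Kinesia-ONE score" among the primary efficacy variables, as a change from Baseline to Visit 2. Section 8.1.1.2 gives the derivation: "In addition, a composite Kinesia-ONE score will be calculated as the average of following scores". Twelve scores follow: three tremor scores (rest, postural, kinetic) and nine task scores (speed, amplitude and rhythm of finger tapping, hand grasp and rapid alternating movement). The availability rule is: "The composite score will only be calculated if at least 50% of the scores are available".

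The two sections name the variable differently. I take them to mean the same one, because the only other average over Kinesia-ONE scores is the separately listed finger tapping speed and rest tremor average.

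SAP 3.1 defines the change: "The change from Baseline is the post-Baseline value minus the Baseline value". The only missing-value condition on it is at the level of the visit value: "If the Baseline or post-Baseline value is missing, then the change from Baseline is set to missing". SAP 8.1.2 sets the analysis: "The change from Baseline to Visit 2 in each of the Kinesia-ONE scores will be analyzed using ANCOVA", and "The efficacy analysis will be performed on the FAS and observed cases will be utilized". Protocol 12.6 adds: "In general, there will be no imputation of missing data". No section fills a missing Kinesia-ONE component or limits the change to components seen at both visits.

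**The concern.** A change score should compare like with like. Here a subject can have 12 components averaged at Baseline and a subset of 6 to 11 averaged at Visit 2, or the reverse. If the components sit at different levels in that subject, removing some of them moves the mean on its own. The difference then enters the ANCOVA as if it were a change in motor symptoms. If the gap is at Baseline, the covariate is displaced as well.

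The SAP does not leave this open for its other multi-item scores. UPDRS Part III (8.1.1.1) is missing if any item is missing, so both visits contain the same items. PDQ-39 (8.2.2) and PAM-13 (8.2.3) also have an availability threshold, but they replace the missing items. The Kinesia-ONE composite has a threshold and no rule for the gaps.

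At stake is the estimated group difference for one listed primary variable, with about 20 subjects per group.

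**Working it through.** The plan gives no figure to reproduce; SAP 2.4 states that there is no formal sample size estimation.

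**Inputs from the documents.** 12 components (3 tremor, 9 task); minimum 50%, so 0.5 × 12 = 6; change = Visit 2 value minus Baseline value; observed cases; about 20 subjects per group.

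**Inputs assumed.** The gap between components within a subject, shown over 0.5 to 2 points, and the number of components missing. The documents give no component levels, score range, SD or missingness rate.

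**Formula.** Let m components be missing at one visit only, with every component value unchanged. Let R be the mean of the retained components, M the mean of the missing ones, and d = R − M.

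- Full composite = [(12 − m)R + mM] / 12
- Reduced composite = R
- Reduced minus full = (m/12) × d

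This is the false change if the gap is at Visit 2. The sign reverses if the gap is at Baseline. It is zero when d = 0.

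| Missing at one visit | d = 0.5 | d = 1.0 | d = 1.5 | d = 2.0 |
|---|---|---|---|---|
| 1 of 12 | 0.04 | 0.08 | 0.13 | 0.17 |
| 3 of 12 | 0.13 | 0.25 | 0.38 | 0.50 |
| 6 of 12 (the most allowed) | 0.25 | 0.50 | 0.75 | 1.00 |

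**Worked subject (assumed values, same at both visits).** Tremor scores 0.5, task scores 2.0. Rest tremor and finger tapping average (0.5 + 2.0)/2 = 1.25, which meets the entry criterion of more than 1.0 in Protocol 6.1.

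- Baseline, all 12: (3 × 0.5 + 9 × 2.0)/12 = 1.625
- Visit 2 without the three tremor scores (9 of 12 = 75%, so the rule is met): 18/9 = 2.000
- Change: +0.375, with nothing changed

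Reading the rule with a fixed divisor of 12 does not help: 18/12 − 1.625 = −0.125.

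**Is a gap of this order possible?** Protocol 6.1 requires bradykinesia but makes rest tremor one of several alternatives. A subject with rest tremor 0 can meet the entry criterion only if finger tapping averages above 2.0. That covers two of the 12 components. It shows that a gap of about 2 points is admissible, not that it is common.

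**Group level.** With d = 1 and three missing, the shift per subject is 0.25. One affected subject of 20 in one arm moves that group mean by 0.25/20 = 0.0125, and two move it by 0.025. With the worked subject's 0.375, one, two or four of 20 move it by 0.019, 0.038 or 0.075.

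**The case against.** The strongest reply is that this will rarely matter. Kinesia-ONE is an in-clinic battery performed in triplicate. Losing several components at one visit while at least six survive is an unusual partial failure, and if the whole battery is missed the composite is simply missing. Rest tremor and finger tapping speed must exist at Baseline for eligibility to be checked. Both arms follow the same in-clinic procedure, so gaps have no evident reason to differ by arm and would mainly add noise. The composite is one of 15 Kinesia-ONE variables. It is not in the protocol's list (4.1.1) and was added by SAP Amendment 1. The individual scores have their own ANCOVAs, which this rule does not touch, and by-subject listings would let a discordant composite be traced. SAP 4.5 calls all tests exploratory.

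All of this stands as a limit on size. None of it makes the derivation like-for-like.

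A reader might infer more than the documents support in three ways:

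- That the change is wrong whenever the component sets differ. It is not: the formula gives zero when retained and missing components have equal means.
- That a shift of 0.13 to 0.50 is large because entry requires a score above 1.0. That threshold is an eligibility level for the average of rest tremor and finger tapping. It is neither a change criterion nor a measure of the composite's variability.
- That the group comparison is biased. That would need gaps that differ between arms, and nothing in the documents points to this.

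**Conclusion.** The point holds as a defect in the derivation rule. As written, the composite change can be non-zero for a subject in whom no component changed, provided the component sets differ between visits and the retained and missing components have different means. The Baseline covariate does not correct this, and the Per-Protocol repeat in SAP 8.1.4 inherits the same derivation.

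The consequence is small. Shifts per subject are a fraction of a point for one to three missing components, and the group-mean shifts worked above are a few hundredths of a point or less, even with all affected subjects placed in one arm. These sizes rest on assumed component gaps and counts of missing components; the documents supply neither. If no components are missing, the defect has no effect. It is still worth correcting, because the study is meant to give an impression of effect from about 40 subjects and the correction is cheap.

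**What to change.** Add to SAP 8.1.1.2: for the composite change from Baseline, and for the Baseline composite used as its ANCOVA covariate, compute both visits' composites only from components non-missing at both visits, and require at least 6 such common components. Keep the by-visit descriptive summaries under the existing 50% rule, so that Baseline summaries do not depend on what was observed at Visit 2.

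In the worked subject, both visits then use the nine task scores and the change is 2.000 − 2.000 = 0. Subjects with complete data are unaffected.

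Costs:

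- A short addition to the text and a small programming change, including a second version of the Baseline composite.
- A few subjects with fewer than 6 common components lose the composite change, and only that.
- Where components are missing, the mean change need not equal the difference of the displayed visit means, so the table needs a footnote.
- Subjects may still differ from one another in which components they contribute. The fix removes the within-subject artefact, not that heterogeneity.

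Requiring all 12 components at both visits would remove both, as the UPDRS Part III rule does, but would give up the 50% tolerance.

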### **8.1.1.3 Number of Neupro dose changes**

The number of Neupro dose changes is derived as the sum of all Neupro dose changes during the treatment period and includes any increase or decrease of dose, irrespective of the dose level. If a dose level change, e.g. from 2mg/24h to 4mg/24h, occurs multiple times, it is counted as often as it occurs.

